¹⁴Both the investigator and the subject will assess each Target DPN Lesion for symptoms associated with irritation. At Visit 2 and Visit 4, the investigator will assess the Target DPN Lesions prior to application of the study medication and 20 (\pm 4) minutes after treatment with the study medication. At Visit 2 and Visit 4, the subject will assess the Target DPN Lesions prior to application of the study medication and 10 (\pm 4) minutes after the treatment of the study medication.

¹⁵A-101 study medication will be applied by the treating physician. All Target DPN Lesions will be treated with study medication following enrollment at Visit 2. If a Target DPN Lesion meets the criteria for re-treatment as defined in Section 7.5, the lesion will be re-treated at Visit 4. Following application of study medication, subjects must NOT wash/submerge the Target DPN Lesions for at least 6 hours and they must NOT apply any topical products to the Target DPN Lesions for at least 6 hours.

¹⁶All subjects will be required to apply Aquaphor to all Target DPN Lesions the morning after study medication application. Sites will be provided supplies of Aquaphor by the Sponsor.

¹⁷All concomitant therapies including (topical and oral) prescription medications, over the counter medications and natural supplements and non-drug therapies including chiropractic, physical therapy, and energy-based therapy must be documented in the subject CRF. Subjects must not apply any topical products (e.g. moisturizers, sunscreen, etc.) to their Target Lesions within 12 hours prior to any study visit.

¹⁸The reporting period for Serious Adverse Events (SAEs) begins when the subject signs the informed consent. Refer to Section 10 for instructions on the reporting of SAEs. Non-serious clinical adverse events will be collected following the application of the study medication at Visit 2. Non-serious adverse events that occur between the time of consent and study medication application will be documented as medical history. All safety reporting (AEs and SAEs) will conclude at Visit 5 (approximately 21 days after last study medication application) except for clinical adverse events related to local skin reactions. These events will be collected through V8.

Table 3: Study Procedures for Cohort 2 Subjects

Visit	V1 Screening	V2	V3	V4	V5	V6	V7	V8
Treatment Day	-13 to 0	1	15	22	29	50	78	106
Treatment Window	N/A	N/A	+ 4 days	+ 2 days	+4 days	± 7days	± 7 days	± 7 days
Study Procedures								

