¹⁵A-101 study medication will be applied by the treating physician. All Target DPN Lesions will be treated with study medication following enrollment at Visit 2. Subjects randomized to ARM B will be required to have their Target DPN Lesions medically abraded prior to treatment with A-101 study medication. If a Target DPN Lesion meets the criteria for re-treatment as defined in Section 7.5, the lesion will be re-treated at Visit 3, and Visit 5. Following application of study medication, subjects must NOT wash/submerge the Target DPN Lesions for at least 6 hours and they must NOT apply any topical products to the Target DPN Lesions for at least 6 hours.

¹⁶All subjects will be required to apply Aquaphor to all Target DPN Lesions the morning after study medication application. Sites will be provided supplies of Aquaphor by the Sponsor.

¹⁷All concomitant therapies including (topical and oral) prescription medications, over the counter medications and natural supplements and non-drug therapies including chiropractic, physical therapy, and energy-based therapy must be documented in the subject CRF. Subjects must not apply any topical products (e.g. moisturizers, sunscreen, etc.) to their Target Lesions within 12 hours prior to any study visit.

¹⁸The reporting period for Serious Adverse Events (SAEs) begins when the subject signs the informed consent. Refer to Section 10 for instructions on the reporting of SAEs. Non-serious clinical adverse events will be collected following the application of the study medication at Visit 2. Non-serious adverse events that occur between the time of consent and study medication application will be documented as medical history. All safety reporting (AEs and SAEs) will conclude at Visit 5 (approximately 21 days after last study medication application) except for clinical adverse events related to local skin reactions. These events will be collected through V8.

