9.2. Vital signs

Vital signs will be measured by a qualified staff member at Visit 1, Visit 2 prior to randomization, Visit 4 (cohort 1 ONLY) prior to treatment and at Visit 8. The following items will be measured:

- Body temperature
- Pulse rate
- Respiration rate

- Blood pressure (systolic and diastolic) after the subject sits quietly for at least 5 minutes
- Height (at Visit 1 only)
- Weight (at Visit 1 only).

Any measure that is, in the opinion of the investigator, abnormal AND clinically relevant (CR) must be recorded as history if found prior to the first study medication treatment or as an AE if found after the first study medication treatment begins (Section 10.1).

A systolic blood pressure >140mm Hg or a diastolic blood pressure >90mm Hg is considered abnormal and therefore must be defined as CR or not clinically relevant (NCR) on the CRFs.

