10.1.3. Adverse event reporting period

The investigator must start reporting non-serious AEs starting with the subject’s first study medication treatment continuing until Visit 6. Non-serious adverse events that occur between the time the subject was consent and the first application of study medication will be reported as medical history.

Reporting for SAEs begins after the subject signs the informed consent and continues until Visit 6 (regardless of relationship to study medication). If a subject experiences a SAE after Visit 6 that is deemed to be related to study medication, the investigator must report this to the Sponsor using the study specific SAE report form.

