10.2. Reporting Procedures

10.2.1. Procedures for reporting adverse events

At each post enrollment visit, the investigator or designee will question the subject to elicit AEs using a non-directive question such as “Has there been any change in your health since the previous study visit?”

The investigator or designee will monitor the subject for at least 20 minutes after the Treatment Completion Time at Visit 2 and at Visit 4 to elicit AEs in a similar manner.

If appropriate, based on the subject's response to non-directed questioning regarding AEs, the investigator or designee will follow-up with directed questions and appropriate evaluations.

Any AE noted during the reporting period must be reported in the source documents and on the appropriate AE CRF.

AEs that are defined as “Not Related” to the study medications will be followed until they are resolved or until the subject’s last study visit. AEs that are defined as “Related” to the study medications will be followed until they are resolved or, if not resolved after the subject’s last study visit, until in the opinion of the investigator, the AE reaches a clinically stable outcome with or without sequelae.

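### Footnote 18 ends AE reporting at Visit 5, against the rest of the plan and its own 21-day figure, and the SAP's AE overview has no line for collected events that start more than 30 days after last treatment

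*Protocol*

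**What the plan says.** **End of reporting.** Footnote 18 annotates the AE row in Protocol Section 6, Tables 2 and 3, and is repeated in SAP 2.1, Tables 1 and 2. It says that all AE and SAE reporting "will conclude at Visit 5 (approximately 21 days after last study medication application) except for clinical adverse events related to local skin reactions". Of the excepted AEs it says: "These events will be collected through V8". The row it annotates is marked from Visit 2 to Visit 6.

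Protocol 10.1.3 has non-serious AEs reported from the "first study medication treatment continuing until Visit 6", and SAEs from consent to the same visit. It adds a later duty: "If a subject experiences a SAE after Visit 6 that is deemed to be related to study medication", the sponsor must be told. SAP 2.4.3.2 and SAP 3.7.3 also stop at Visit 6. None of these carries the skin-reaction exception.

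**Findings at later visits.** Protocol 9.3 draws blood at Visits 1 and 8 only. It makes a clinically significant out-of-range result an AE whenever it is found after treatment has begun. Protocol 9.2 measures vital signs at Visit 1, "Visit 2 prior to randomization, Visit 4 (cohort 1 ONLY) prior to treatment and at Visit 8". A clinically relevant abnormality there is recorded as history, "or as an AE if found after the first study medication treatment begins (Section 10.1"). SAP 2.4.3.4 repeats that rule without the cross-reference. Protocol 10.2.1 adds: "At each post enrollment visit, the investigator or designee will question the subject to elicit AEs".

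**Analysis.** SAP 3.7.3 limits treatment-emergent events to 30 days after the last treatment, and all ten overview lines are TEAE or TESAE lines. Protocol 12.4 promises a tabulation of laboratory abnormalities judged clinically relevant; SAP 3.7.4 describes only values and changes. SAP 3.7.2 tabulates LSR grades 1 to 4, while the scale in Protocol 9.1 and SAP 2.4.3.1 runs from 0 to 3.

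**The concern.** Safety is part of the primary objective, and SAP Section 4 says that the abbreviated report keeps the full safety content. Two things follow.

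First, sites have conflicting instructions on when to stop reporting. Read literally, footnote 18 ends the reporting of non-skin AEs on the very day that a Cohort 2 subject receives a third treatment. The conflict matters in practice because Protocol 10.2.2 ties the investigator's SAE duties to events within the AE reporting period.

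Second, the plan collects some events that its AE overview cannot count. The measurements at late visits are summarized elsewhere. What has no stated place is the late event as an AE, with its severity, seriousness and relationship to treatment.

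**Working it through.** **Inputs.** Visit days and windows come from the schedule tables; the 30-day limit comes from SAP 3.7.3.

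- Cohort 1: Visit 2 Day 1; Visit 4 Day 22 to 26; Visit 5 Day 29 to 36. Possible last treatment: Visit 2 or 4.
- Cohort 2: Visit 2 Day 1; Visit 3 Day 15 to 19; Visit 5 Day 29 to 33. Possible last treatment: Visit 2, 3 or 5.
- Both: Visit 6 Day 43 to 57 (nominal 50); Visit 8 Day 99 to 113 (nominal 106).

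**Step 1: the footnote's 21 days.** Days from last treatment = Visit 5 day − last treatment day.

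| Cohort, last treatment | Nominal | With windows |
|---|---|---|
| 1, Visit 2 | 29 − 1 = 28 | 28 to 35 |
| 1, Visit 4 | 29 − 22 = 7 | 29 − 26 = 3 to 36 − 22 = 14 |
| 2, Visit 2 | 29 − 1 = 28 | 28 to 32 |
| 2, Visit 3 | 29 − 15 = 14 | 29 − 19 = 10 to 33 − 15 = 18 |
| 2, Visit 5 | 29 − 29 = 0 | 0 |

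No row contains 21. On nominal days the figure is reproduced only by Visit 6 after a Day 29 treatment: 50 − 29 = 21. For Cohort 1, Visit 6 after a Day 22 treatment gives 50 − 22 = 28.

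**Step 2: when the TEAE window closes.** Last treatment day + 30: 1 + 30 = Day 31; 15 + 30 = Day 45; 22 + 30 = Day 52; 29 + 30 = Day 59. The latest possible close is 33 + 30 = Day 63. The earliest Visit 8 is Day 99, so Visit 8 comes at least 99 − 63 = 36 days after the window for every subject treated within the visit windows.

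**Step 3: days up to Visit 6 that lie outside the window.**

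| Last treatment | Nominal | With windows |
|---|---|---|
| Day 1 | 50 − 31 = 19 (Days 32 to 50) | 43 − 31 = 12 to 57 − 31 = 26 |
| Day 15 | 50 − 45 = 5 (Days 46 to 50) | 0 to 57 − 45 = 12 |
| Day 22 | 0 (50 < 52) | 0 to 57 − 52 = 5 |
| Day 29 | 0 (50 < 59) | 0 (57 < 59) |

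These days are lost from the overview only if reporting runs to Visit 6. If Visit 5 governed, the nominal loss would be zero, because Day 29 precedes Day 31.

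**Step 4: scheduled checks between first treatment and the close of the window.** Laboratory: none in either cohort. Vital signs: none in Cohort 2, one in Cohort 1 (Visit 4). The only post-treatment laboratory sample, and in Cohort 2 the only post-treatment vital signs, therefore fall at Visit 8, after either stated end of AE reporting and after the TEAE window.

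**The case against.** The best reply is that the conflict is a stale visit number. All four footnotes are one copied text, which itself sends the reader to Section 10 for SAEs; Section 10.1.3, the AE rows and both SAP sections agree on Visit 6; and 21 days fits Visit 6 for a third Cohort 2 treatment. That explains how the error may have arisen. It does not remove it: the SAP carries the footnote forward unchanged, 21 days is still wrong for Cohort 1 on nominal days, and the skin-reaction exception appears nowhere else.

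Several stronger readings are tempting and do not hold.

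- *That AE reporting runs to Visit 8 because subjects are questioned at every visit.* Protocol 10.2.1 requires recording only of AEs noted within the reporting period. Questioning at Visits 7 and 8 also serves follow-up of open events and the late related-SAE duty, so it does not extend the period.
- *That every AE found at Visit 8 is lost from the analysis.* If Visit 6 governs, it is open whether a Visit 8 finding is a reportable AE at all; the vital-sign rule points to Section 10.1, which contains that limit. A finding given an earlier onset inside the window could also count. Visit 8 laboratory values, vital-sign changes, abnormal blood pressure counts and LSR grades are summarized in any case.
- *That the SAP dropped the abnormal-laboratory table.* SAP Section 4 removes no safety output. The table is unspecified, not withdrawn.

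It is also fair that the protocol synopsis leaves safety endpoints to the SAP, that a 30-day TEAE definition is a legitimate choice, and that the SAP's general sentence on summaries by organ class and preferred term is not expressly limited to TEAEs. Finally, Protocol 7.5 calls for retreatment of any lesion graded above 0 unless an exception applies, so the 19-day gap concerns only subjects whose lesions were all clear, exempt or refused.

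**Conclusion.** Two items are wrong as written: footnote 18, whose Visit 5 cut-off conflicts with the Visit 6 passages and whose 21 days matches no possible Visit 5 interval; and the LSR grades 1 to 4, set against a 0 to 3 scale.

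The rest is a gap in specification. The overview in SAP 3.7.3 has no line for:

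- AEs collected up to Visit 6 that start after the window, if Visit 6 governs;
- related SAEs after the window, which Protocol 10.1.3 requires to be reported;
- Visit 8 laboratory or vital-sign findings, if these are reportable AEs with onset dated at Visit 8.

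The day counts assume that visits and treatments keep to their windows. The documents give neither a rate of late AEs nor the share of subjects treated once, so the number of events affected is unknown and, with 36 subjects, may be small. The point is worth fixing because safety is a primary objective and the remedy is cheap. The documents do not support a claim that late safety data are uncollected or unreported as a whole.

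**What to change.** 1. Reconcile footnote 18 in all four tables, including its 21-day figure and its Visit 8 skin-reaction exception, with Protocol 10.1.3, SAP 2.4.3.2, SAP 3.7.3 and the AE rows. Which end of reporting governs is for the sponsor to state.
2. Say how the laboratory and vital-sign AE rules (Protocol 9.2 and 9.3, SAP 2.4.3.4) apply at Visit 8 under the reconciled period.
3. In SAP 3.7.3 keep the 30-day TEAE definition, and add one table or listing of collected AEs and SAEs with onset or worsening after it.
4. In SAP 3.7.4 specify the laboratory table promised in Protocol 12.4, or list its removal in SAP Section 4.
5. In SAP 3.7.2 tabulate LSR grades 0 to 3.

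The cost is wording plus two small outputs, with no new visits. Whether skin-reaction AEs to Visit 8 would be additional data depends on which passage is taken to govern. The late-event counts will not be comparable with TEAE counts, because collection rules differ after Visit 6, and the table should say so.

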7. STUDY TREATMENT

7.1. Investigational Study Medication

The study medication for this study is A-101 Solution 40%. The study medication solution is clear and colorless solution.

Table 4 Study Medication Information

Study Medication Name	A-101 Solution 40%
Manufacturer	James Alexander Corporation, Blairstown NJ
A-101 concentration (%)	40
Pharmaceutical Form	Solution
Storage Conditions	59°F to 77°F (15°C to 25°C) protected from excessive heat, open flame and combustibles, out of direct sunlight and in a well-ventilated, dry area
Route	Topical
Application	Safety glasses and nitrile or vinyl examination gloves must be worn during the application process. Latex gloves are prohibited.
Duration of Administration	Apply study medication to each Target Lesion for approximately 15 seconds. Allow each Target Lesion to remain undisturbed for approximately 60 seconds. Repeat the application/waiting cycle until the study medication has been applied to each Target Lesion up to 3 times.

7.2. Subject randomization

Cohort 1 of this study is an open label study. Subject randomization is not applicable for this part of the study.

Subjects that are determined to be eligible for treatment in Cohort 2 will be randomized in a 1:2 ratio to one of the following treatment arms.

- ARM A: A-101 40% Solution; No medical abrasion to the Target DPN Lesions
Treatment Days 1, 15 and 29
- ARM B: A-101 40% Solution applied after medically abrading the Target DPN Lesions;
Treatment Days 1, 15 and 29

7.3. Study medication packaging, storage and dispensing

A-101 Solution 40% will be provided by Aclaris Therapeutics, Inc. and labelled according to the local law and legislation.

The study medication will be packaged in single use applicators. Each single-use applicator consists of a crushable glass ampoule that contains 1.5 milliliters (mL) of study medication. The ampoule is provided inside a sealed polyethylene tube with a flocked, doe foot applicator on one end.

The investigational site will be supplied with a lot of A-101 Solution 40% labelled appropriately for the study. Investigational sites will be required to maintain full drug accountability for all applicators that are received at the site.

A-101 study medication must be stored in a location where there is limited access to the investigational study medication at 59°F to 77°F (15°C to 25°C) protected from excessive heat, open flame and combustibles, out of direct sunlight and in a well-ventilated, dry area.

Investigational study medication supplies are only to be used for subjects properly consented and enrolled to this study.

7.4. Drug Accountability

The investigator or designee will maintain an accurate record of the receipt of the study medications as shipped by Aclaris Therapeutics, Inc. (or designee), including the date received and the condition of the study medications. One copy of this receipt will be returned to Aclaris Therapeutics, Inc. (or designee) when the contents of the study medication shipment have been verified and one copy maintained in the study file. In addition, an accurate study medication disposition record will be kept, specifying the amount dispensed for each subject and the date of dispensing. This inventory record will be available for inspection at any time. At the completion of the study, the original inventory record will be available for review by Aclaris Therapeutics, Inc. upon request.

Final drug accountability will be completed by the study monitor at the completion of the study and all unused study medication will be returned to Aclaris Therapeutics, Inc. drug depot for disposal per Aclaris Therapeutics, Inc. (or designee's) written instructions.

7.5. Study Medication Treatment

The study medications are for external, topical use on the DPN Target Lesions on the appropriate study subject only.

The treating investigator performing the study medication treatments must comply with the study medication handling warnings. In cohort 1, the treating physician will apply the A-101 Solution 40% to each DPN Target Lesion at Visit 2 and at Visit 4, if applicable.

At Visit 4, any Target Lesion that has a Physician DPN Lesion Assessment **grade of >0** and **ONLY DPN Target Lesions that have a Physician DPN Lesion Assessment grade of >0**, must receive study medication treatment UNLESS either of the following criteria apply to the DPN Target Lesion:

- The DPN Target Lesion has a Visit 4 pre-treatment LSR grade of 3 (severe) for any sign or symptom AND the grade has increased compared to the Visit 3
- The DPN Target Lesion is, in the investigator's opinion, not appropriate for a retreatment (the investigator must note the reason on the subject's Comments CRF page).

[figure not shown]
In cohort 2, for those subjects randomized to ARM B, the treating physician will medically abrade the Target DPN Lesion prior to apply the A-101 study medication. All subjects in cohort 2 will be allowed to have up to 3 treatment applications of the A-101 study medication. If subjects meet the criteria as outlined above, subjects in cohort 2 may receive 2 additional study medication applications at Visit 3 (Day 15) and Visit 5 (Day 29).

7.5.1. Preparing the Study Medication for Application

To perform a study medication treatment for a DPN Target Lesion a staff member will select the appropriate study medication applicator. Then follow these instructions:

- Prepare for the treatment:
 - Wash your hands prior to, and after completing the study medication treatments
 - Wear safety glasses and nitrile or vinyl examination gloves during the treatment; **latex gloves are prohibited**
 - Visually inspect the applicator for damage:
 - If the applicator appears damaged do not use it for the treatment, contact the study monitor for disposal instructions and select an unused applicator with the next highest number for the treatment
 - If the applicator is intact, proceed with the treatment process.
- Activate and prime the applicator:
 - Hold the applicator horizontally with the tip/cap end pointing away from the subject and any staff; ensure the applicator tip protective cap is firmly attached
 - Place the thumbs and forefingers of both hands on the applicator tube at the point on the applicator where indicated
 - Gently but firmly squeeze the applicator tube with your fingers until the glass ampoule is crushed, you should hear an audible "SNAP"
 - Repeatedly squeeze the applicator tube moving your finger location up and down the tube to the tip and back again 2 or 3 times to ensure the glass ampoule containing the study medication has been completely crushed
 - Examine the applicator tube and tip for any wetness or leaking (if the applicator is damaged do not use it for the treatment, contact the study monitor for disposal instructions and select an unused applicator with the next highest number for the treatment)
 - Hold the applicator in one hand and orient it vertically with the TIP FACING DOWN

- With your other hand, gently flick or tap the applicator tube to ensure any air bubbles have been displaced and the study medication flows downward toward the tip
- Remove the applicator tip protective cap
- Hold the applicator with one hand over a disposable paper free absorbent material (e.g., gauze pad), place your thumb and forefinger approximately 0.5 inch above top of the finger grip on the applicator tube and gently and repeatedly squeeze the applicator tube until you see a drop of study medication visible in the opening of the holed applicator tip. The flow of study medication may be controlled by gently squeezing to apply pressure to the sides of the applicator tube to express more study medication, and by releasing pressure on the tube slow or stop the delivery of the study medication
- The applicator is now ready to use in a treatment. Refer to Figure 2 for a visual diagram of the steps needed to prepare the A-101 study medication applicator.

[figure not shown]

Figure 2: Diagram Showing the Process for Preparing the A-101 study medication applicator

